### **5.5 Safety Population**

The Safety population includes all randomized subjects who receive at least 1 actual dose of the study treatment (ITT population). The population will be analyzed according to the treatment that the subjects actually received study drug regimen, rather than the treatment to which the subjects were randomized.

Note that, as this is an open-label study, it has been observed that one subject received cefiderocol after completing the randomization assigned study treatment of BAT,. This subject will be included in the Safety Population as having received BAT. However, a limited number of key safety analyses will be repeated with this subject assigned to the cefiderocol arm. (see [section 10.1.1](#) for details).

### **5.6 Pharmacokinetic Concentration Population**

The Pharmacokinetic (PK) Concentration population includes all subjects who undergo plasma sampling and have at least 1 evaluable PK assay result for cefiderocol. This population will be used for the concentration listing, plotting of the concentration-time data, and the concentration summary.

## 6. STATISTICAL CONSIDERATIONS FOR DATA ANALYSES AND HANDLING

### 6.1 Statistical Reporting

In this SAP, unless otherwise stated, summary statistics include the number of subjects, arithmetic mean, standard deviation (SD), minimum, median, and maximum. SAS® (Version 9.2 or later version) will be used for all statistical analyses. If the APACHE II score is corrected after randomization, the corrected score will be used in the analysis.

### 6.2 Statistical Testing

No inferential testing will be performed except for the exploratory analysis described in Section 9.4.1.7. If statistical tests are performed, they will be performed at the 0.05 significance level using 2-sided tests, except where otherwise noted. No multiplicity adjustment of statistical tests will be applied in this study.

### 6.3 Analysis Windows

Measurements for efficacy or safety endpoints will be performed according to the schedule as shown in Section 4.4. The following analysis window (Table 6-1) will be used for analysis at a particular visit or time point to be included in by-visit summary statistics for the specified variables. Day 1 is defined as initial day of administration of drug.

If there are multiple available values in an analysis time window, the closest value to the target day captured from scheduled visit or unscheduled visit will be used for analysis, and if there are multiple values within the same day, the latest value will be used.

**Table 6-1 Analysis Window**

Time Point	Target Day	Analysis Time Window
Early Assessment	Day 3 or 4	Not applicable
End of Treatment	End of last infusion	Not applicable
Test of Cure	Date of end of last infusion + 7	-2 to + 2 days
Follow-up	Date of end of last infusion + 14	-3 to + 3 days
PK sampling		
Just prior to the next infusion	Next infusion start date and time	-1 to 0 hours
1 hour after the infusion	Infusion start date and time + 1hr	± 15 minutes
At the end of infusion	Infusion end date and time	-15 minutes to end of infusion
1 hour after end of infusion	Infusion end date and time + 1hr	± 0.5 hours
Premature EOT	Start date and time of last infusion	Within 24 hours after last dose

EOT = End of Treatment; PK = pharmacokinetic

Pharmacokinetic samples that are collected before the sixth dose administration will not be used for the summary of plasma cefiderocol concentrations (Pharmacokinetic samples just prior to the sixth dose will be included.). The target of the second PK sampling will be within 24 to 72 hours after the dosing adjustment. The target of PK sampling for premature EOT will be within 24 hours of the last dose.

For all values including values obtained at an unscheduled visit, the analysis time window above will be applied. Values other than considered as TOC or FU, obtained at visit reported as EA and EOT will be used for analysis at EA and EOT, respectively. If a subject is received study drug more than 21 days, Day 21 will be considered as the date of end of last infusion. Unscheduled visits within an analysis time window for scheduled visit will be used to provide values for that scheduled visit.

## 6.4 Missing Data

### 6.4.1 Missing or Partial Dates and Times

For classification of prior and concomitant medications, if the medication cannot be classified into concomitant medications or prior medications due to a partially missing date, the rules below will be applied for the classification. This rule will be applied for collection time of laboratory data as well if time is missing.

For start date:

- If the year and month are observed but the day is missing, the first day of the month will be used.
- If the year is observed but the month is missing, the first day of the year, 01 Jan, will be used.

If the year is observed but the time is missing, the first time of the day, 12:00 AM, will be used. And, for end date:

- If the year and month are observed but the day is missing, the last day of the month will be used.
- If the year is observed but the month is missing, the last day of the year, 31 Dec, will be used.
- If the year is observed but the time is missing, the end time of the day, 23:59 AM, will be used.

If micro sample collection time is missing, the end time of the day, 23:59 AM, will be used.

The imputed dates will not be displayed in the listings.

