## **6. RESTRICTIONS**

### **6.1 Prior Therapy**

Prior therapies are defined as therapies which were taken prior to randomization of the study.

Systemic antibiotic treatment or prophylaxis for Gram-negative pathogens including aerosolized antibiotics in patients with HAP/VAP/HCAP must be stopped before administration of study drug.

Prior antibiotic therapy (oral or intravenous) taken by patient during the current during the current hospitalization until randomization into the study will be recorded in the eCRF and the information will include the name of drug used or procedures done, start and end dates, route of administrations and reason.

Similarly, any prior therapy other than systemic antibiotics (prescription drugs, over-the-counter drugs, procedures [eg, surgical or non-surgical related to infection treatment or treatment-related complications such as dialysis] with or without any medication) taken by patient within 2 weeks prior to randomization of the study will be recorded in the eCRF.

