#### **6.4.2 Missing Microbiological or Clinical Outcome**

For clinical and microbiological outcomes, subjects who are lost to follow-up or have missing or "indeterminate" outcomes will be included in the denominator as indeterminate for cure/eradication rate, i.e., considered as not responders. If judged by the investigator that a subject died due to pneumonia, BSI/sepsis or cUTI, the clinical outcome will be considered as clinical failure after the event of death. If a subject died due to other reasons, the clinical outcome will be considered as "indeterminate" after death.

For clinical outcome, if a subject received additional antibiotics for target disease (i.e., baseline infection) before the target date, the outcome will be considered as "clinical failure". If a subject did not receive additional antibiotics for target disease before the target date, the outcome will be considered as "indeterminate".

Missing values for other individual data points will remain as missing unless otherwise specified. All analysis will be based on observed case unless otherwise stated.

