## **6.8 Additional Antibiotics**

Additional antibiotics are defined as systemic antibiotics with Gram-negative activity. The medical group will determine which medications have Gram-negative activity. If the route of administration is ophthalmic, transdermal, nasal, topical, or vaginal, the medication will not be considered as a systemic antibiotic. Concomitant medications ending before initial study treatment start date/time plus 3 hours will not be considered as additional antibiotics. Antibiotics for Gram-negative pathogens that are allowed to be received (see Clinical Study Protocol [Section 5.2.1.1](#)) from Day 1 or Day 2, they will not be considered as additional therapy, but if they are received on Day 3 or after, they will be considered as additional therapy.

Medical monitor will adjudicate additional antibiotics based on the available data if needed.

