### **8.4 Prior Therapy and Concomitant Therapy Other Than Best Available Therapy/Adjunctive Antibiotics**

Prior and concomitant medications will be coded using the WHO Drug Dictionary. If a subject received cefiderocol as concomitant medication, this will be reported as cefiderocol. Prior medications are defined as medications that were taken prior to the first dose date/time of the study drug. Concomitant medications are defined as medications that were taken on or after the first dose date/time of the study drug.

The number and percentage of subjects taking concomitant medications or procedures will be summarized by ATC and PT for each treatment group for the CR Micro-ITT population and Safety population. Although a subject may have taken 2 or more medications, the subject is counted only once within an ATC classification. The same subject may contribute to 2 or more PTs in the same classification. Prior medications or procedures will be summarized in the same manner for the CR Micro-ITT population and Safety population.

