#### **9.1.3.2 cUTI**

- **Eradication:** A urine culture shows the baseline Gram-negative uropathogen found at entry at  $\geq 10^5$  CFUs/mL are reduced to  $< 10^3$  CFUs/mL.
- **Persistence:** A urine culture shows that the baseline Gram-negative uropathogen found at entry at  $\geq 10^5$  CFUs/mL grows  $\geq 10^3$  CFUs/mL.
- **Indeterminate:** No urine culture obtained from an appropriate clinical specimen or additional antibacterial therapy for the treatment of the current infection.

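### In cUTI, a prior antibiotic stopped on Day 1 with no recorded stop time can turn documented eradication into a primary non-response

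*SAP*

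**What the plan says.** **Data on prior antibiotics.** Protocol 6.1 says that prior Gram-negative therapy "must be stopped before administration of study drug". For prior antibiotics it names as data items the drug, "start and end dates, route of administrations and reason". No clock time is listed.

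**Imputation.** SAP 6.4.1 opens its rule with "For classification of prior and concomitant medications, if the medication cannot be classified into concomitant medications or prior medications due to a partially missing date". For end dates it then says: "If the year is observed but the time is missing, the end time of the day, 23:59 AM, will be used".

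**Classification.** SAP 8.4: "Concomitant medications are defined as medications that were taken on or after the first dose date/time of the study drug".

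**Additional antibiotics.** SAP 6.8 counts systemic drugs active against Gram-negative bacteria, with two exemptions:
- "Concomitant medications ending before initial study treatment start date/time plus 3 hours will not be considered as additional antibiotics".
- Agents permitted under protocol 5.2.1.1 do not count on Day 1 or 2. That section's list applies to the cefiderocol arm, in pneumonia or BSI/sepsis only. It excludes polymyxins, cephalosporins and carbapenems, and cUTI patients on cefiderocol receive monotherapy.

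SAP 6.8 closes by leaving adjudication to the medical monitor where needed.

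**Consequence.** For cUTI, SAP 9.1.3.2 defines Indeterminate as "No urine culture obtained from an appropriate clinical specimen or additional antibacterial therapy for the treatment of the current infection". SAP 6.4.2 keeps Indeterminate patients in the denominator as non-responders. SAP 9.3.1 makes eradication at TOC the primary outcome for cUTI.

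**The concern.** The three-hour allowance in SAP 6.8 appears meant to avoid penalising the ordinary switch from a prior regimen to study treatment. The 23:59 imputation works against it. It puts an untimed Day 1 stop at the latest possible moment, when a patient who followed protocol 6.1 stopped before the first dose. For that patient the imputed time is wrong, and the error runs through to the cUTI primary endpoint, overriding a urine culture that shows eradication.

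Such records are foreseeable. Patients who failed an empiric regimen are eligible, and general exclusion 11 allows up to 24 hours of potentially effective therapy in cUTI. The cUTI group is small, so a few false flags would show in the rate.

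**Working it through.** **1. Rule chain for a cUTI patient.** Assume that a carbapenem was started before entry for the index infection and stopped on Day 1 before the first dose, that only the stop date was recorded, and that the TOC urine culture shows eradication.

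| Step | Source | Result |
|---|---|---|
| Stop time missing | SAP 6.4.1 | Stop set to Day 1, 23:59 |
| Stop falls after first dose | SAP 8.4 | Concomitant |
| Three-hour exemption | SAP 6.8 | Applies only if 23:59 is earlier than first dose + 3 h |
| Day 1-2 exemption | SAP 6.8, protocol 5.2.1.1 | No cover in cUTI |
| Counted as additional therapy | SAP 9.1.3.2 | Indeterminate |
| Indeterminate | SAP 6.4.2, 9.3.1 | Primary non-response |

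**2. When the exemption fails.** It fails if first dose + 3 h is at or before 23:59, so if the first dose is at or before 20:59. That is 20 h 59 min out of 24 h = 1259/1440 = 87% of the clock. It is 87% of patients only if first doses are spread evenly over the day, which is an assumption.

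**3. Group sizes.** 150 × 2/3 = 100, which reproduces the plan's approximate number treated with cefiderocol. The cUTI cap gives at most 0.30 × 150 = 45 patients, or 30 cefiderocol and 15 BAT at 2:1. CR Micro-ITT can be smaller.

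**4. Effect of one false flag in an eradicated patient.** 1/30 = 3.3 points on cefiderocol and 1/15 = 6.7 points on BAT.

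**5. Illustration at an assumed true eradication rate of 60%,** with Clopper-Pearson 95% intervals as in SAP 9:

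| Arm | False flags | Rate | 95% CI |
|---|---|---|---|
| Cefiderocol | 0 | 18/30 = 60.0% | 40.6 to 77.3 |
| Cefiderocol | 1 | 17/30 = 56.7% | 37.4 to 74.5 |
| Cefiderocol | 2 | 16/30 = 53.3% | 34.3 to 71.7 |
| Cefiderocol | 3 | 15/30 = 50.0% | 31.3 to 68.7 |
| BAT | 0 | 9/15 = 60.0% | 32.3 to 83.7 |
| BAT | 1 | 8/15 = 53.3% | 26.6 to 78.7 |

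**6. Range.** The documents give no flag rate. Expected responders lost = n × true rate × flag rate. With true rates of 50% to 70% and flag rates of 5% to 20%, both assumed, cefiderocol loses 30 × 0.50 × 0.05 = 0.75 to 30 × 0.70 × 0.20 = 4.2. BAT loses half as many, about 0.4 to 2.1.

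**7. Direction.** With a true rate of 60% in both arms, the bias in cefiderocol minus BAT is 0.60 × (BAT flag rate − cefiderocol flag rate):
- 10% in both arms: 0 points.
- 10% cefiderocol, 0% BAT: −6 points.
- 5% cefiderocol, 10% BAT: +3 points.

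**8. Other infection sites.** The primary outcome in pneumonia and BSI/sepsis is the investigator's clinical assessment (SAP 9.1.1). SAP 6.4.2, under its heading for missing outcomes, says that "if a subject received additional antibiotics for target disease (i.e., baseline infection) before the target date, the outcome will be considered as" clinical failure. The next sentence makes a patient without such antibiotics Indeterminate, which makes sense only where the outcome is missing. The pair therefore chooses between two kinds of non-response. At these sites the flag reaches only secondary results: microbiological outcome (SAP 9.1.3.1, 9.1.3.3) and the composite, where cure with eradication changes from Response to Indeterminate (SAP Table 9-2).

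**The case against.** **The link is partly inferred.** SAP 6.4.1 is worded for prior/concomitant classification, and 6.8 does not say that its three-hour test uses imputed times. This stands as a caveat. But that classification is the entry to 6.8, and the SAP revision record shows the missing-time logic and the additional-antibiotic definition entering together in version 2.0. If 6.8 does not use the imputed time, it has no rule for an untimed stop, so it needs a sentence either way.

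**Times may have been collected.** Protocol 6.1 need not be the full eCRF specification, and the SAP compares medications with a first-dose date and time. Missing times may therefore be few. That limits the size of the problem but does not correct the rule.

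**SAP 9.1.3.2 requires therapy for the current infection and does not cite 6.8.** True, and reason for use is recorded. But a prior drug given for the qualifying infection carries exactly that reason, so the field does not remove it.

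**The medical monitor can correct errors.** The step is discretionary, takes place in an open-label study, and has no written criterion for untimed stops. Imputed dates are also not shown in listings. It may rescue some patients but does not replace a rule.

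**A reader might infer that the error falls mainly on cefiderocol.** BAT patients can keep a prior drug as part of BAT, which points that way. But a prior drug replaced when BAT starts is imputed identically, and the Day 1-2 exemption rests on a list written for the cefiderocol arm. The 2:1 allocation gives more cases on cefiderocol, not a higher rate. The documents do not settle the direction.

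**A reader might also infer that cures in pneumonia or BSI/sepsis become primary failures, or that most patients are exposed.** Step 8 of the working shows why the first does not follow. For the second, empiric failure is one of several entry routes in protocol 4.1, and nothing says how many patients stop a prior drug on Day 1.

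**Conclusion.** The fault is real and confined, for the primary endpoint, to cUTI. The stated rules can score a compliant, eradicated patient as a non-responder because a clock time was not recorded. The supplementary cUTI microbiological definitions (SAP 9.2.4.2 and 9.3.2.2) would not expose it, because both still treat additional antibacterial therapy as Indeterminate.

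The cost is 3.3 points per false flag on cefiderocol or 6.7 points on BAT if the cUTI cap is filled, and more per patient if CR Micro-ITT is smaller. The number of flags and the net direction between arms are unknown. The conclusion assumes that SAP 6.8 uses the imputed stop time, that some Day 1 stops are untimed, and that adjudication does not catch them all. The primary analysis is descriptive, so what is at stake is the reported rate and its interval, not a test. The correction is cheap and worth making.

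**What to change.** In SAP 6.8, for both arms:

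- Treat a Gram-negative antibiotic that was started before the first dose, and has a Day 1 stop date with no stop time, as ended at the first dose.
- Count it as additional only if its stop date is Day 2 or later, or a recorded stop time is more than 3 hours after the first dose, subject to the existing Day 1-2 exemption.
- Report the number of such untimed Day 1 stops by arm.
- Add a cUTI sensitivity analysis of the primary endpoint under the 23:59 rule.

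The 23:59 rule can stay for its other uses. The cost is a short addition to the SAP, a small programming change and one extra table. The downside is that a genuine untimed overlap of a few hours on Day 1 would not be flagged in the main analysis. The sensitivity analysis shows how much that could matter.

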- Patient is known to be colonized (as evidenced by prior cultures from the same site as the infection) with a carbapenem-resistant Gram-negative pathogen prior to developing acute infection, ie, prior culture within the previous 72 hours

The possible pathways for enrollment in the study are presented in Figure 4-1.

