## **7. STUDY PROCEDURES AND METHODS OF ASSESSMENTS**

In the case that a patient is screened and enrolled on the same day, the information requirements for the Screening (Day –2 to Day 1) and for Randomization (Day 1) are to be completed. The requirements for the complete physical examination, vital signs, and clinical laboratory tests will be limited to only one set of tests.

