## **7.7 Clinical Laboratory Tests**

### **7.7.1 Microbiologic Cultures**

Appropriate clinical specimens will be obtained from all patients within 48 hours prior to the start of the infusion of the first dose of study treatment or clinical specimens obtained by the site within the 48 hours prior to signing ICF could be acceptable as screening/baseline cultures for this study.

For patients who failed empiric treatment (as defined in general inclusion No. 4), clinical specimens obtained within 72 hours of randomization in this study could be used as screening/baseline cultures. A culture should be done again upon randomization and the pathogen isolated sent to central lab.

Biologic tissue or fluids for microbiologic cultures will be sent to the local laboratory for identification of all pathogens causing the infection. After initiation of study treatment, appropriate clinical specimens will be obtained at the specified assessment time points (EA, EOT, TOC, FUP. If it is not possible to obtain an appropriate clinical specimen after randomization, the reason (eg, no material available to culture) must be documented in the eCRF.

In addition, 2 blood samples from separate venipunctures will be obtained from all patients regardless of the site of infection, within 48 hours prior to the start of study treatment and sent to the local laboratory. Subsequent blood cultures are to be repeated only if the baseline blood culture is positive.

Culture results should be recorded in the eCRF with the date of sampling and the reporting date and identified isolates sent to the central lab.

In general, all specimens should also have Gram stain of infected material (not swab). A report of both inflammatory cells and bacteria is necessary.

Inappropriate clinical specimens should not be used for confirmatory culture identification of causative pathogens.

Detailed procedures (Gram stain, quantitative or semi-quantitative cultures) per infection type are provided in Appendix 4.

All isolated pathogens (Gram-positives, Gram-negatives, fungi and yeast) will be frozen and stored for later shipping to the central laboratory. Detailed procedures for sample

collection, handling, labeling, storage, and shipping will be provided in the separate study procedure manual. Shipping labels, instructions for shipping, and courier service will be provided from the sponsor or CRO.

[figure not shown]

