#### **7.7.1.1 Diagnostics for Initial Patient Qualification**

Patients are eligible for randomization only if there is documented evidence of a carbapenem-resistant Gram-negative pathogen from a suitable infection source. Routine culture methods with susceptibility phenotype determination (MIC, Etest, or disc diffusion) using standard determination of susceptibility (breakpoints) based on local regulations would meet eligibility criteria. Isolates considered intermediate, but not fully susceptible, will be considered carbapenem-resistant.

In order to expedite appropriate treatment for the patient before the availability of standard susceptibility results, rapid diagnostic methods, or selective chromogenic media may be used to identify patients with carbapenem-resistant pathogens. These may include marketed tests to determine the presence of carbapenem hydrolyzing enzymes (carbapenemases) or tests to determine the presence of genes indicating the presence of carbapenemases (polymerase chain reaction [PCR]) (Figure 7-1). Tests available to the investigator through their local microbiology laboratory may be used. Investigational rapid diagnostics may be provided and can be used to determine a patient's eligibility for inclusion into this study. A manual with details on investigational rapid diagnostics that may be provided along with instructions for use will be provided separately. Rapid diagnostic result should be recorded in the eCRF.

Although the rapid diagnostic tests may provide evidence of eligibility of patients for this study, all patients will require subsequent confirmation through microbiologic isolation and susceptibility testing of isolates obtained from appropriate clinical specimens. The final study analysis will use the pathogen identification and susceptibility data provided by the central microbiology laboratory.

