#### **6.5 Baseline Definition**

- For microbiological endpoints, baseline pathogens are determined from appropriate clinical specimens collected within the 3 days prior to randomization in this study for subjects who have been treated previously with an empiric antibiotic regimen and failed treatment, both clinically and microbiologically (as defined in general inclusion number 4). For the other subjects, baseline pathogens are determined from appropriate specimens collected within the 48 hours prior to the start of the first infusion of study treatment. Clinical specimens obtained by the site within the 2 days prior to signing informed consent form could be acceptable as screening/baseline cultures for this study. If appropriate specimens are collected on multiple dates before the first infusion, the specimens collected on the latest date for each pathogen will be used to determine baseline pathogens.

If multiple specimens are collected within the above time range for baseline, the following rules will be applied:

- In case same Gram-negative pathogens with different quantification are obtained from multiple samples from the same specimen type (i.e., blood, urine, respiratory specimen, or infection site that caused septic shock) that qualified a patient eligible for this study, the pathogen with the highest quantification/classification is considered as the baseline pathogen. The priority of quantitation is listed below:
  1. Highest value in quantification
  2. Largest value in semiquantification
  3. Largest value in no-quantification
- In case same Gram-negative pathogens with same quantification are obtained from different specimens, the pathogen with the highest minimum inhibitory concentration (MIC) for 1. cefiderocol 2. Meropenem, 3. Imipenem, 4. colistin is considered as the baseline pathogen.

The appropriate clinical specimen type is sputum, tracheal aspirate, bronchoalveolar lavage (BAL) fluid, protected specimen brush, pleural fluid, lung biopsy for HABP/VABP/HCABP, blood for BSI/sepsis, or urine for cUTI. Tissue from primary infection site is also applicable for all baseline infection. Specimen that was collected from other site may be considered as appropriate specimen. This will be determined by the medical monitor.

Only for subjects with cUTI, the pathogen whose quantification is  $10^5$  colony-forming units (CFUs)/mL or more will be considered as baseline pathogen.

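### Two SAP data-handling rules (6.7 in cUTI, and 6.4.1) can, in rare cases, void a patient's only valid baseline pathogen and drop the patient from the primary population

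*SAP*

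**What the plan says.** **Populations.** Micro-ITT needs a baseline Gram-negative pathogen (SAP 5.2). CR Micro-ITT, the primary efficacy population (SAP 9), is a subset of Micro-ITT with central confirmation of resistance (SAP 5.3). CR-ME is a subset of CR Micro-ITT (SAP 5.4).

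**Baseline window, SAP 6.5.** For patients who did not fail empiric therapy, "baseline pathogens are determined from appropriate specimens collected within the 48 hours prior to the start of the first infusion of study treatment". For empiric failures the source is "specimens collected within the 3 days prior to randomization in this study". A further clause says that site specimens obtained "within the 2 days prior to signing informed consent form could be acceptable as screening/baseline cultures". In cUTI only, a baseline pathogen must reach 10^5 CFU/mL.

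**Missing time, SAP 6.4.1.** "If micro sample collection time is missing, the end time of the day, 23:59 AM, will be used". There is no exception for a specimen known to precede dosing.

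**Name mismatch, SAP 6.7.** If the two laboratories name the pathogen differently, the central name is used and the count becomes missing. SAP 6.4.2 leaves other missing values missing.

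**How the situations can arise.** Protocol 7.7.1 wants culture results "recorded in the eCRF with the date of sampling and the reporting date and identified isolates sent to the central lab"; it names no time. Protocol section 7 gives instructions "In the case that a patient is screened and enrolled on the same day". Entry need not wait for a susceptibility result: "rapid diagnostic methods, or selective chromogenic media may be used to identify patients with carbapenem-resistant pathogens" (protocol 7.7.1.1), and known colonisation counts "as evidenced by prior cultures from the same site as the infection" (protocol 4.1).

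**The concern.** Membership of the primary population should depend on whether the patient had a resistant pathogen before treatment. Under these rules it can depend on a blank clock field or on a corrected organism name.

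In cUTI, a urine culture that met the entry count can lose that count because the central laboratory renamed the organism, although the specimen and its measured count are unchanged. Separately, an untimed culture taken before the first dose on Day 1 is timed at 23:59 and becomes post-dose. If the affected isolate was the only qualifying one, the patient leaves Micro-ITT, CR Micro-ITT and CR-ME together.

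The added population, CR Micro-ITT 2 (SAP 5.3.1), does not clearly restore either patient. It still needs a baseline pathogen, which the untimed culture no longer supplies, and it uses local resistance only where central data are absent. After a name mismatch, central data exist.

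**Working it through.** **1. The plan's own figure.** 150 x 2/3 = 100, which reproduces the stated approximately 100 patients on cefiderocol; BAT is 150/3 = 50. Nothing below depends on a power statement, and the plan gives none.

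**2. Name mismatch in cUTI.** SAP 6.7 makes the count missing; SAP 6.4.2 leaves it missing; SAP 6.5 needs 10^5 CFU/mL or more. The renamed isolate therefore cannot be a baseline pathogen. The patient is lost unless another carbapenem-resistant uropathogen with an intact count remains. By contrast, for an isolate never shipped to the central laboratory, SAP 6.7 keeps the local name and treats only the MIC as unknown.

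**3. Missing time against the 48-hour window.** Gap = first-infusion time minus specimen time; accepted if 0 to 48 h. Example: culture at 08:00, infusion at 14:00 on the same date. The true gap is 6.0 h; with 23:59 imputed it is about -9.98 h, so the culture is rejected. On a grid of ten-minute steps for both times:

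| Specimen date relative to first infusion | Truly in window | In window after 23:59 |
|---|---|---|
| Same date, pre-dose | 100% | 0% |
| One day before | 100% | 100% |
| Two days before | 50.3% | 100% |
| Three days before | 0% | 0% |

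So the rule loses only same-date specimens. It also admits untimed specimens dated two days before dosing, of which 49.7% of the grid are truly more than 48 h before.

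**4. Do the other clauses of SAP 6.5 rescue the same-date culture?** Grid: 96 quarter-hour infusion times on Day 1, and consent at each of 193 quarter-hours from 48 h before the infusion up to it (96 x 193 = 18,528 combinations). Randomisation is on Day 1, no later than the infusion.

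| Clause | By clock | By calendar date |
|---|---|---|
| 48 h before infusion | 0/18,528 | written in hours |
| 2 days before consent, consent on Day 1 | 0/4,656 | 4,656/4,656 |
| 2 days before consent, consent earlier | 0/13,872 | 0/13,872 |
| 3 days before randomisation (empiric failures) | 0/18,528 | 18,528/18,528 |

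Grid counts show which cases pass; they are not frequencies.

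**5. Date or clock?** For these two clauses protocol 7.7.1 uses 48 hours and 72 hours. SAP 6.5 restates them as 2 days and 3 days but keeps hours for the infusion window. That favours a date reading, though the SAP does not say so.

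**6. Size of one lost patient.** Planned cell sizes: pneumonia 0.50 x 150 = 75, split 50/25; cUTI at its cap 0.30 x 150 = 45, split 30/15. Response near 50% is assumed. Intervals are Clopper-Pearson (SAP 9): the lower limit is the 2.5% quantile of Beta(x, n-x+1) and the upper limit the 97.5% quantile of Beta(x+1, n-x).

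| Cell | All kept (95% CI; width in points) | Responder lost | Non-responder lost | Shift, points |
|---|---|---|---|---|
| BAT cUTI | 8/15 = 53.3% (26.6-78.7; 52.1) | 7/14 = 50.0% | 8/14 = 57.1% | 3.3-3.8 |
| BAT pneumonia | 13/25 = 52.0% (31.3-72.2; 40.9) | 12/24 = 50.0% | 13/24 = 54.2% | 2.0-2.2 |
| Cefiderocol cUTI | 16/30 = 53.3% (34.3-71.7; 37.3) | 15/29 = 51.7% | 16/29 = 55.2% | 1.6-1.8 |
| Cefiderocol pneumonia | 26/50 = 52.0% (37.4-66.3; 28.9) | 25/49 = 51.0% | 26/49 = 53.1% | 1.0-1.1 |

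BSI/sepsis is not illustrated. Its entry criteria (protocol 4.4.3.2 and 4.4.3.4) already require an identified or isolated resistant pathogen, so the qualifying specimen will normally predate Day 1.

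**The case against.** The strongest reply is that these cases are very rare. Empiric failures and BSI/sepsis patients normally have an earlier culture, and colonised patients may have an in-window one. SAP 6.5 works pathogen by pathogen, so an earlier isolate keeps the patient in. That stands, and it is why the point is limited to patients with no other qualifying isolate.

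A reader might infer that every patient screened and dosed on the same day with an untimed culture is lost. The documents do not support this. Same-day screening normally means consent on Day 1, and the day-worded pre-consent clause, read by date, keeps all of those patients. A reader might also infer from protocol 7.7.1 that untimed cultures are common. Silence about a time shows only that they are possible: sample collection and labelling are detailed in a separate procedure manual, and data queries may fill the gaps.

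On the count, it is fair to say that a local count belongs to the organism as locally named, and that moving it to another organism could be wrong. That holds where two isolates cannot be told apart. It is weak where the urine grew one Gram-negative isolate and that isolate was shipped. SAP 6.5 does rank unquantified results when choosing among specimens, but its cUTI sentence is more specific. The medical monitor's discretion in SAP 6.5 concerns specimen site, not timing or a missing count.

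**Conclusion.** The point holds as a minor one. The SAP 6.7 route is clear on the text and confined to cUTI. The SAP 6.4.1 route depends on how SAP 6.5 is read. By date, the remaining loss is patients who are not empiric failures, consented before Day 1 and have no earlier in-window isolate. By clock, Day 1 consenters and empiric failures without an earlier qualifying isolate are exposed too.

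The documents give no frequency for missing times or name mismatches, so the number affected may be zero. One lost patient moves a pneumonia or cUTI rate by about 1 to 4 points, against full-cell intervals 29 to 52 points wide; this assumes planned randomised sizes and response near 50%.

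It would be tempting to call this a bias for or against cefiderocol. The documents do not support that: both rules act on pre-treatment data identically in each arm, and 23:59 can add specimens as well as remove them. The primary analysis is descriptive, and affected patients remain in the ITT mortality and safety analyses.

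**What to change.** - **SAP 6.7:** carry the local count to the central name when the shipped isolate matches a single local isolate, for example one Gram-negative organism in the urine. Set it to missing only when no match can be made, for example with two uropathogens, which protocol 4.4.2.3 allows.
- **SAP 6.4.1:** treat an untimed specimen recorded as screening/baseline and dated on the first-infusion date as pre-dose; keep 23:59 for all others.
- **SAP 6.5:** state that the pre-consent and 3-day windows are applied by calendar date.

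The cost is a few sentences and a small derivation change, with no new data collection. The downside is that a culture taken just after the first dose may occasionally be accepted as baseline. The change does not touch the admission of untimed specimens dated two days before dosing, so the SAP should acknowledge that tolerance.
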